5.1 Case report form

The main purpose is to obtain the necessary information for the research plan in a complete, accurate, clear, and timely manner. The data in the medical record report form should be consistent with the original file. The filling out of the medical record report form must be complete and clear (using a black or blue ballpoint pen, in compliance with legal document requirements). The medical record report form is a regulatory document that must be suitable for submission to hospital authorities.

All revisions and corrections must be made and confirmed by the researcher, specifying the date of revision/correction. Errors must be clearly retained and cannot be covered with corrected data (such as using correction fluid). The researcher must indicate the reasons for revising important data. The missing data/notes in the medical record should be replaced by underline in the blank input of the medical record report form to avoid unnecessary follow-up investigations.

5.2 Research documents and preservation

Researchers should have a document outlining the research objectives. This file should include all necessary documents for conducting the research. After the research is completed, these documents should be archived according to relevant regulations of the hospital and the country.

5.3 Regulations on data management and data traceability

The designed CRF is in triplicate (carbonless), and the second copy of the CRF is submitted to the data management personnel participating in this clinical trial to establish a unified database. After completing at least 5 CRFs, the trial will be promptly submitted to the data administrator through clinical monitoring to establish the corresponding database. All data will be entered in duplicate using computer software to develop a data entry program.

During this period, the questionnaire will be forwarded to the researchers for data review through clinical monitors, and the researchers should answer and return it as soon as possible. The locked data file cannot be changed again. The database will be handed over to statistical analysts for statistical analysis according to the requirements of the statistical plan. Submit the statistical analysis report to the main researcher of this experiment to write the research report.

Provide training to researchers on relevant regulations and SOPs, and ensure that all researchers strictly comply with them to record truthfully, timely, accurately, and completely, prevent omissions and arbitrary modifications, and avoid forging or fabricating data; Inspectors strengthen the verification of various records. The follow-up medical records of the subjects should be kept together with the CRF as the original data. Each center's laboratory department provides participation in the quality control of the Ministry of Health's clinical laboratory center

The certificate of conformity shall be stored in the computer connected to the inspection equipment for at least three years for future reference.

5.4 data privacy

All records related to the identity of the subjects shall be kept confidential and shall not be disclosed to the public beyond the scope permitted by relevant laws and/or regulations.

6 , informed consent

Explanation on Informed Consent

1) Patient obtaining informed consent: The research team will provide detailed research information to potential participants, including research objectives, procedures, potential risks, and benefits. The informed consent process will be conducted in a private and quiet environment to ensure that patients are not under any pressure. Researchers will answer all questions from patients and ensure that they fully understand the research content. The informed consent form will be signed by the patient themselves after fully understanding the research content. If the patient is unable to sign it in person, the legal guardian will sign it on their behalf.

2) Measures for obtaining informed consent from vulnerable groups:

For patients without legal capacity, such as hospitalized patients with serious illnesses and patients with mental illnesses, an informed consent form will be signed by their legal guardians.

For illiterate individuals, verbal consent will be used and a witness will be present to sign and certify.

Special attention will be paid to the autonomy of prisoners, individuals with cognitive impairments, and other disadvantaged groups, ensuring that they are not subjected to any form of coercion or inducement.

For students, staff of our institution, etc., we will ensure that their participation in the research is voluntary and that they will not receive any additional benefits from participating in

the research. For patients with mental/cognitive disorders, a psychiatrist will assess whether they have self-awareness and determine the method of obtaining informed consent based on this assessment.

The process of signing/obtaining informed consent forms

Provision of informed consent form: The research team will provide potential participants with a written informed consent form, which will detail all relevant information about the study.

Explanation of informed consent: Researchers will explain each item in the informed consent form to participants to ensure their full understanding.

Question and Answer: Researchers will give participants the opportunity to ask questions and answer all questions during the explanation process.

Sign informed consent form: After participants fully understand the research content and agree to participate, they will be invited to sign and date the informed consent form.

The person in charge of obtaining informed consent: The acquisition of informed consent forms will be the responsibility of a trained research coordinator or principal investigator (PI).

Time and location: Informed consent will be given at a designated location in the hospital prior to participants being enrolled in the study.

Handling of special circumstances: For participants who are unable to personally sign the informed consent form, appropriate measures will be taken, such as video calls or recorded phone calls, to ensure that they can provide informed consent.

Throughout the entire research process, we will respect the rights of each participant and ensure that they are free to raise questions, opinions, or choose to withdraw from the study at any time. We will regularly review the informed consent process to ensure that it always complies with ethical standards and legal regulations.

7 , Adverse Event Reporting

7.1 Definition

AE refers to any adverse medical event that occurs from the signing of the informed consent form by clinical trial subjects until 90 days after the last use of the study treatment, regardless of whether there is a causal relationship with the trial treatment, and is determined as an adverse event.

7.2 Content

- 1) The aggravation of pre-existing medical conditions/diseases (including symptoms, signs, and laboratory abnormalities) prior to entering clinical trials;

2) Any newly occurring adverse medical events (including symptoms, signs, newly diagnosed diseases);

3) Abnormal laboratory test values or results with clinical significance.

Researchers should record in detail any adverse events (AEs) that occur in the subjects, including the name of the AE and a description of all related symptoms, the time of occurrence, severity, correlation with the investigational drug, duration, measures taken, and final results and outcomes.

7.3 Adverse Event Record

Researchers should carefully observe any adverse reactions that occur in subjects during the clinical study period, require subjects to truthfully report changes in their condition after treatment, avoid inducing questions, and record in detail in the case form CRF, including the time of occurrence, symptoms, signs, degree, duration, laboratory test indicators, treatment methods, process, results, etc. of adverse reactions, and record in detail the situation of concomitant medication.

7.4 Criteria for determining the severity of adverse events

Refer to the grading standards for drug adverse events in NCI-CTCAE 5.0 version.

7.5 Criteria for determining the relationship between adverse events and investigational drugs

AE includes all unexpected clinical manifestations, as long as these events occur after signing the informed consent form, regardless of whether they are related to the experimental treatment, they should be reported as AE. During the treatment period, any discomfort or abnormal changes in objective laboratory test indicators reported by the subject should be recorded truthfully, and the severity, duration, treatment measures, and outcome of the AE should be indicated. The research physician should also comprehensively determine the relationship between the AE and the investigational drug, and evaluate the possible association between the AE and the investigational treatment according to the five level classification system of "definitely related, possibly related, possibly unrelated, definitely unrelated, and unable to determine" Definitely related "," possibly related ", and" unable to determine "are all listed as adverse drug reactions, and the determination criteria are shown in the following table:

Table 1 Criteria for Judging the Relationship between AE and Experimental Treatment

Grading criteria

Definitely related: the occurrence of the event conforms to a reasonable chronological order after treatment, and the event conforms to the known reaction type of the suspected drug;

Alternatively, if the condition improves after discontinuing the medication and the event occurs again after repeated administration.

Possible correlation: The occurrence of events follows a reasonable chronological order after treatment, and the events do not conform to the known reaction type of the suspected drug; The patient's clinical condition or other treatment methods may also cause this event.

Possible unrelated: The occurrence of the event does not conform to a reasonable chronological order after treatment, the event does not conform to the known response type of the suspected drug, and the patient's clinical status or other treatment methods may have caused the event.

Definitely unrelated: The occurrence of the event does not conform to a reasonable chronological order after treatment, the event does not conform to the known response type of the suspected drug, the patient's clinical status or other treatment methods may cause the event, the event disappears after disease improvement or discontinuation of other treatment methods, and the event occurs when other treatment methods are repeatedly used.

Unable to assess: There is no clear relationship between the occurrence of the event and the time sequence after treatment, and it is similar to the known reaction types of the drug. Other drugs used at the same time may also cause corresponding events.

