2.2 Secondary research objectives

2.2.1 Evaluate the impact of intensified adjuvant therapy on 1-year and 2-year overall survival rates and quality of life in patients with newly diagnosed glioblastoma who undergo partial surgical resection or short-term recurrence progression.

2.2.2 Evaluate the safety and incidence of radiation necrosis in newly diagnosed glioblastoma patients undergoing enhanced adjuvant therapy with surgical partial resection or short-term recurrence progression.

3, Research design and methodology:

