Stupp+PD-1/CTLA-4 dual antibody group: Starting 2-6 weeks after surgery, synchronous TMZ radiotherapy and chemotherapy will be performed. After completing synchronous radiotherapy and chemotherapy for 28 days, TMZ combined with PD-1/CTLA-4 dual antibody will be used as adjuvant therapy. PD-1/CTLA-4 dual antibody 6mg/kg intravenous infusion once, with a cycle of 14 days.

Modified Stupp group: Starting 2-6 weeks after surgery, synchronous TMZ radiotherapy and chemotherapy will be performed. For partially resected lesions or short-term recurrence and progression lesions after surgery, high-dose PGT 66Gy/30Gy will be given locally. PTV1 in high-risk areas around the tumor bed will be 60Gy/30F, and in low-risk areas will be 54Gy/30F. After completing synchronous radiotherapy and chemotherapy for 28 days, 6 cycles of adjuvant TMZ chemotherapy will be started.

This study is divided into three stages: screening period, treatment period, and follow-up period. The screening period is 2-6 weeks after surgery. Treatment period: Subjects who meet the inclusion criteria but do not meet the exclusion criteria will receive postoperative intensive adjuvant therapy after signing the informed consent form. Follow up period: After stopping the study treatment, the subjects enter the follow-up period. Follow up period: Head MRI examination and evaluation will be conducted at baseline, postoperative, before radiotherapy, and after radiotherapy. MRI enhanced scans will be performed every month during the follow-up period to observe PFS until the end of the follow-up period. For subjects who have not withdrawn their informed consent form, survival information (i.e. date and cause of death, subsequent tumor treatment, etc.) will be collected every month through telephone and/or clinical visits.

This study is expected to have an enrollment period of 24 months and a follow-up period of 24 months.

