SAE occurring 90 days after the last use of the study drug is generally not reported unless suspected to be related to the study drug. SAE should provide detailed records of symptoms, severity, correlation with the investigational drug, occurrence time, treatment time, measures taken, follow-up time and methods, as well as outcomes. If researchers believe that a certain SAE is not related to the investigational drug but potentially related to the study conditions (such as termination of the original treatment or comorbidities during the trial), this relationship should be detailed in the narrative section of the SAE report form. If the intensity of an ongoing SAE or its relationship with the investigational drug changes, a follow-up report should be submitted immediately.

6) Follow up of SAE

All SAEs should be followed up until disappearance, remission to baseline level or \leq level 1, and stability.

Researchers should be followed up until the end of AE, stable status, reasonable explanation, loss to follow-up, or death; Follow up information should be provided promptly according to the requirements of the sponsor.

If there are no specific requirements in the protocol, AE/SAE collection and follow-up usually begin after the subjects sign the informed consent form, and each AE/SAE must be followed up during the study period; At the end of the study, the collection and follow-up principles for AE/SAE that occurred after the final treatment of the subjects can refer to the following table:

Classification, collection, recording, and follow-up

All SAEs should be followed up until disappearance, remission to baseline level or \leq level 1, and stability.

Researchers should be followed up until the end of AE, stable status, reasonable explanation, loss to follow-up, or death; Follow up information should be provided promptly according to the requirements of the sponsor.

If there are no specific requirements in the protocol, AE/SAE collection and follow-up usually begin after the subjects sign the informed consent form, and each AE/SAE must be followed up during the study period; At the end of the study, the collection and follow-up principles for AE/SAE that occurred after the final treatment of the subjects can refer to the following table:

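### Causality criteria and the late-SAE rule are written for drugs, so toxicity of the modified Stupp arm's radiotherapy boost cannot be properly attributed and may escape late reporting

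*Protocol*

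**What the plan says.** Section 3.1 gives radiotherapy and TMZ to all four arms. Two arms add a bispecific antibody in the adjuvant phase. The modified Stupp arm adds no drug; what it adds is local radiotherapy: "high-dose PGT 66Gy/30Gy will be given locally". Section 2.2.2 makes safety and radiation necrosis a secondary objective: "Evaluate the safety and incidence of radiation necrosis".

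Section 7.5 names two objects of the causality judgement in one sentence. The first is the drug: "The research physician should also comprehensively determine the relationship between the AE and the investigational drug". The second is the treatment: the physician is to "evaluate the possible association between the AE and the investigational treatment according to the five level classification system". The table is titled "Criteria for Judging the Relationship between AE and Experimental Treatment".

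The rules inside the table are narrower:
- The first route to *definitely related* requires that "the event conforms to the known reaction type of the suspected drug". The second route requires improvement when a medication is stopped and recurrence when it is given again.
- *Possible correlation* requires plausible timing, that "the events do not conform to the known reaction type of the suspected drug", and that the patient's condition or another treatment could also be the cause.
- Definitely related, possibly related and unable to determine are all classed as adverse drug reactions.

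The recorded item is also drug-only. Section 7.2 and section 7.6(5) both ask for "correlation with the investigational drug". Section 7.6(5) adds that SAEs arising beyond 90 days after the last study drug are generally reported only when a link to the study drug is suspected. Section 7.1 counts its 90 days from the last study *treatment*; 7.6(3) and 7.6(5) count from the last study *drug*.

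**The concern.** A causality scheme has to be able to give the right answer for the component under test. In one of the three experimental arms that component is radiotherapy, yet each operative rule asks about a drug: known reaction type, dechallenge and rechallenge, output label, recorded item, late-reporting trigger.

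Two things are at stake. The first is the attribution of boost toxicity, which bears on how objective 2.2.2 is interpreted. The second is whether serious radiation events that appear late enter the SAE reports at all. Attribution is judged when the event occurs and is hard to reconstruct afterwards, so these rules need to be right before patients are treated.

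**Working it through.** The plan gives no figure to reproduce on this point. The check is to apply the rules as written to one case, then to date the reporting window.

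**Step 1. Radiation necrosis in the modified Stupp arm, run through Table 1.** Assume plausible timing after radiotherapy.

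| Grade | What the table requires | Does it fit? |
|---|---|---|
| Definitely related, first route | Plausible timing and a known reaction of the suspected drug | No, unless drug is read to include radiotherapy |
| Definitely related, second route | Improvement on stopping a medication, recurrence on repeating it | No; written for a drug |
| Possible correlation | Plausible timing, not a known reaction of the drug, another treatment may be the cause | Yes, on every element |
| Possibly unrelated, definitely unrelated | Timing not plausible | No |
| Unable to assess | No clear time relationship, resembles known reactions of the drug | No |

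The highest grade available is possible correlation, and 7.5 then classes the event as an adverse drug reaction. The only drug in this arm is TMZ, which the Stupp arm also receives. The boost, which is what distinguishes the two arms, has no entry of its own.

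**Step 2. When the 90-day limit falls in the modified Stupp arm.** Inputs from 3.1: adjuvant TMZ starts 28 days after chemoradiotherapy ends; there are six 28-day cycles; dosing is on days 1 to 5. The last item, and the cycle length, are stated for the Stupp arm and taken to apply here. TMZ is taken as the study drug, since it is the only drug in the arm.

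- Start of cycle 6, counted from the end of radiotherapy: 28 + 5 × 28 = 168 days.
- Last TMZ dose: 168 + 5 = about 173 days.
- Limit: 173 + 90 = about 263 days after radiotherapy ends.
- If no adjuvant TMZ is given after chemoradiotherapy: 0 + 90 = about 90 days.

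Section 3.1 puts follow-up after study treatment stops and expects it to last 24 months. If that is 24 months per patient, 90 days is about 3 of them, and the remaining 21 or so fall under the conditional rule.

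**Step 3. A serious radiation event after the limit.** There are two possible outcomes:
- The physician attributes it to radiotherapy. No link to the study drug is suspected, so 7.6(5) generally does not call for a report.
- The physician carries over the literal Table 1 grade. The event is reported, but as a suspected drug reaction.

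Neither route reports the event under its likely cause.

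**The case against.** The strongest reply is that 7.5 is not confined to drugs. The same sentence requires a grade against the investigational treatment, and the table's title says experimental treatment. A sensible physician would read the boost as that treatment. This stands to the extent that a reader who infers that causality is judged *only* against the drug, or that boost toxicity is left wholly unattributed, goes further than the text. It does not cure the criteria, because neither route to the top grade can be met by radiotherapy as worded.

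Second, the safety objective does not depend on attribution. Sections 7.1 and 7.5 capture AEs regardless of causality, and modified Stupp differs from Stupp only by the boost, so the comparison of incidence by arm shows what the boost adds. This stands within the AE window. It would be wrong to infer that the incidence of radiation necrosis is lost there.

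Third, a reader might infer that related-event rates are inflated specifically in the antibody arms. The protocol does not support that. It never says which agent is the suspected drug when several are given, and all four arms receive radiotherapy and TMZ, so the same literal reading produces the same label in every arm, control included. Nor does it give a rate of radiation necrosis from which to count affected events.

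Fourth, 7.6(5) has the SAE narrative describe a relation to study conditions when the drug is judged not responsible. This is a partial route: it covers SAEs only, its examples are termination of the original treatment and comorbidities, and it applies only once a report is being written.

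Finally, component fields may exist on the CRF, which is not shown. That cannot be ruled out, but the wording of Table 1 and of the late-SAE rule is fixed in the protocol.

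**Conclusion.** The point holds in this form: the protocol names both drug and treatment as objects of the causality judgement, but every rule that produces a result is written for a drug. For an arm whose sole experimental component is radiotherapy, that gives a wrong result. Boost toxicity is capped at possible correlation and labelled a drug reaction, and a serious radiation event later than about 263 days after radiotherapy is generally unreported when attributed to radiotherapy. The 263 days rests on all six TMZ cycles being given on schedule and on TMZ counting as the study drug; it shortens if TMZ stops early.

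The size is qualitative. It affects the interpretation of safety and the completeness of late SAE reporting, not the efficacy analysis or the sample size. No number of affected patients can be derived from the protocol. It should be corrected because the rule itself misfires, which is more than a missing detail.

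**What to change.** - In 7.2, 7.5 with Table 1, and 7.6, replace the drug wording with *study-treatment component*, defined as radiotherapy (including the boost), TMZ, or antibody.
- Record relatedness separately for each component the patient has received.
- Apply the stop-and-repeat criterion to drugs only.
- Label the resulting category *treatment-related* rather than adverse drug reaction.
- In 7.6(5), extend the trigger for SAEs beyond 90 days to events suspected to be related to any study treatment, radiotherapy included.
- Reconcile the start of the 90-day window: study treatment in 7.1, study drug in 7.6(3) and 7.6(5).

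The cost is a few extra CRF fields per AE, revised wording in three sections, and some additional late SAE reports. No visits or tests are added, and treatment is unchanged.
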